5.5 RGI-C

Changes in the severity of rickets and bowing will be assessed centrally by three independent pediatric radiologists contracted by a central imaging facility using a disease specific qualitative Radiographic Global Impression of Change (RGI-C) scoring system.

The RGI-C is a seven point ordinal scale with possible values:

- +3 = very much better (complete or near complete healing of rickets),
- +2 = much better (substantial healing of rickets),
- +1 = minimally better (i.e., minimal healing of rickets),
- 0 = unchanged,

- 1 = minimally worse (minimal worsening of rickets),
- 2 = much worse (moderate worsening of rickets),
- 3 = very much worse (severe worsening of rickets),

Raters will be presented with side-by-side images taken from subjects during the UX023-CL301 study with the Baseline image on the left (Image A) and Post-Treatment image (Week 40 and Week 64) on the right (Image B). Raters will be asked to evaluate change in Image B for the abnormalities they consider to be present in the Baseline Image A. This exercise will be performed for the distal radius and ulna from the bilateral wrist X-rays, and the distal femur and proximal tibia and fibula from the bilateral knee X-rays at Week 40 and Week 64. At Week 64, Image A (presented on the left) will remain the Baseline image and Image B (presented on the right) will be the post-treatment image from Week 64. In addition to bilateral wrists and knees, the Week 40 and Week 64 RGI-C analysis will include a rating of the full femur, tibia and fibula from the bilateral standing long leg film with the Baseline standing long leg image on the left (Image A) and the Week 40 (or Week 64) standing long leg image on the right (Image B). See data collection form in [Appendix 5](#).

Prior to rating, the three raters will be trained to gain consensus on the terminology used to describe XLH-related radiographic abnormalities and to establish inter-rater reliability. Following the training, each rater will independently complete a quiz involving the rating of practice images to ensure the success of the training and the reliability of scores among the raters. For the Week 40 and Week 64 analysis, each of the three raters will perform the rating exercise at a work station at the central imaging facility. Only one rater can be present at the facility at any given time to prevent group rating or sharing of scores. Each rater will be presented with side-by-side images of the wrist and knee with Baseline on the left (Image A) and Post-Treatment on the right (Image B). Raters will be asked to evaluate the presence of various abnormalities in the wrist and knee in Image A and change in those abnormalities in Image B. At the Week 40 analysis, each rater will evaluate changes in rickets severity from Baseline to Week 40 in the wrists and knees by assigning a regional score for the wrist, a regional score for the knee, as well as an overall impression score. Raters will be blinded to the treatment group and subject's baseline and demographics information. At Week 64, the same process will be followed as Week 40 except that the raters will also evaluate images from long leg radiographs. RGI-C scores will be entered into an EDC system at the time of the scoring and cannot be retrieved or changed by the rater after submission. RGI-C scores will be transferred electronically from the imaging facility to Ultragenyx after the image rating exercise is complete.

The RGI-C scores for the three raters will be averaged and the mean scores for the wrist, knee, overall impression and RGI-C long leg score will be reported. RGI-C response is defined as an averaged RGI-C global score of at least +2.0 (i.e. substantial healing of rickets).

5.6 RSS

The severity of rickets will be measured using a scale developed by [name] for the assessment of nutritional rickets (Thacher et al. 2000). This scale will be referred to as the RSS. The RSS system is a 10-point radiographic scoring method that was developed to assess the severity of nutritional rickets in the wrists and knees based on the degree of metaphyseal fraying, cupping, and the proportion of the growth plate affected. Scores are assigned for the unilateral wrist and knee X-rays deemed by [name] to be the more severe of the bilateral images. The maximum total score on the RSS is 10 points, with a total possible score of 4 points for the wrists and 6 points for the knees. Higher scores indicate greater rickets severity. Each radiograph is scored individually by [name] who will serve as the single central independent rater for all UX023-CL301 X-rays taken at Baseline, Week 40 and Week 64. For the X-rays taken during the UX023-CL301 study, [name] will be blinded to the treatment group and subject's baseline and demographics information. Each rating performed by [name] is entered into an EDC system at the time of the rating and transferred electronically to a central imaging facility. The scores cannot be retrieved from the system by [name] after submission. See RSS data collection form in [Appendix 4](#).

5.7 Growth

5.7.1 Standing height/recumbent length Z-score and Percentile

Recumbent length will be measured in subjects < 2 years old or those unable or unwilling to stand for the measurement. Standing height/recumbent length measurements prior to treatment will be abstracted from medical records where available.

Growth as measured by standing height or recumbent length will be evaluated on a percentile basis using the Centers for Disease Control/National Center for Health Statistics (CDC/NCHS) Clinical Growth Charts (Kuczmarski et al. 2000). Data used to produce the United States Growth Charts smoothed percentile curves will be downloaded from the official CDC/NCHS web site: http://www.cdc.gov/growthcharts/percentile_data_files.htm

The data files from the CDC/NCHS that are used for this analysis are summarized below. These files represent the different growth curves for children. LMS refers to the parameters in the CDC Growth Charts Percentile Data Files used to construct the growth curves; these are: the power in the Box-Cox transformation (L); the median (M); and the generalized coefficient of variation (S).

The data files used are:

- Length-for-age charts, birth to 36 months, LMS parameters and selected smoothed recumbent length percentiles in centimeters, by sex and age (LENAGEINF).
- Stature-for-age charts, 2 to 20 years, LMS parameters and selected smoothed stature percentiles in centimeters, by gender and age (STATAGE).

Calculation of Z-scores for length/stature values above and below the median will be performed. Using the CDC/NCHS Clinical Growth Charts, the height-for-age Z score will be calculated using the following equation:

$$Z = \{(X/M)^L - 1\} / (L \times S),$$

where X is the physical measurement (stature in cm) and the LMS parameters are obtained from the appropriate CDC/NCHS Clinical Growth Chart corresponding to the age in months of the child. The percentile corresponding to the Z score is then the corresponding percentile from the standard normal distribution.

5.7.2 Weight Z-score and Percentile

Weight will be evaluated by z score and percentile using the same method as Section 5.7.1 based on Centers for Disease Control/National Center for Health Statistics (CDC/NCHS) Clinical Growth Charts (Kuczmarski et al. 2000). The data files used for weight Z-score and percentile are:

- Weight-for-age charts, birth to 36 months, LMS parameters and selected smoothed weight percentiles in kilograms, by sex and age (WTAGEINF).
- Weight-for-age charts, 2 to 20 years, LMS parameters and selected smoothed weight percentiles in kilograms, by sex and age (WTAGE).

5.7.3 Growth Velocity

Growth velocity of recumbent length/standing height in cm/year will be assessed by a model-based approach. A linear regression model for each subject will be built based on all recumbent length/standing height measurements by assuming a linear change in growth:

$$Y_t = \beta_0 + \beta_1 X_t + \varepsilon_i$$

Where Y_t is the recumbent length/standing height (cm) measured at Time t ; X_t is the time when recumbent length/standing height is measured; β_0 is the intercept, β_1 is the slope of the regression model; ε_i is random error term.

The growth velocity Z score will be calculated based on Tanner's standard (Tanner et al. 1985) in Appendix 6. Let [T1, T2] denotes the age interval (years) where the growth velocity is estimated from, for example, for post-treatment growth velocity at Week 40, T1 = age (years) at baseline and T2 = age (years) at Week 40. The mid-point of the age interval $(T1 + T2)/2$ will be used to locate the closest reference age in the reference table. The corresponding 50th percentile (Mean) and SD values will be used to calculate the growth velocity Z score in the following equation:

$$\text{Growth velocity Z score} = \frac{\text{Growth velocity} - \text{mean}}{\text{SD}}$$

If $(T1 + T2)/2$ is less than 2.25 years, the growth velocity Z score will not be calculated.

5.8 Percent of Predicted Six-Minute Walk Test

The percent of predicted values will be calculated using published normative data based on age, gender, and height (Geiger et al. 2007). The percent of predicted walking distance 6MWT is given as:

For males:

$$\begin{aligned} & \text{Percent of predicted six minute walk test} \\ &= \frac{\text{Observed 6MWD}}{196.72 + (39.81 * \text{Age}) - (1.36 * \text{Age}^2) + (132.28 * \text{Height})} * 100 \end{aligned}$$

For females:

$$\begin{aligned} & \text{Percent of predicted six minute walk test} \\ &= \frac{\text{Observed 6MWD}}{188.61 + (51.50 * \text{Age}) - (1.86 * \text{Age}^2) + (86.10 * \text{Height})} * 100 \end{aligned}$$

where Age is the subject's age at the time of the assessment (expressed as one digit decimal) calculated using the following: $(\text{date of test} - \text{date of birth})/365.25$, and height is the subject's standing height at the time of the assessment (in m). If there is no height measured at the time of the 6MWT assessment, the closest prior height will be used.

5.9 Health-related Quality of Life (SF-10 for Children Health Survey)

The SF-10 for Children Health Survey (SF-10) is a caregiver-completed questionnaire designed to assess physical and psychosocial health-related quality of life in healthy and ill children (Saris-Baglana et al. 2006). The 10 items were adapted from the Child Health Questionnaire and utilize a 4-week recall period. Responses are used to generate 2 component summary scores: physical summary score (PHS-10) and psychosocial summary score (PSS-10). The scale scores have been centered so that a score of 50 corresponds to the average score in a comprehensive 2006 sample (a combination of general population and supplemental disability and chronic condition samples). Scale scores are standardized to a mean of 50 and a standard deviation of 10 in the combined U.S. general population. The scoring of the SF-10 will be performed according to the method described in (Saris-Baglana et al. 2007). Higher global scores are associated with better quality of life.

5.10 Patient-Reported Outcomes Measurement Information System (PROMIS)

The PROMIS was developed by the National Institutes of Health and uses domain-specific measures to assess patient well-being (Broderick et al. 2013), (NIH 2015). It uses a T-score metric in which 50 is the mean of a relevant reference population and 10 is the standard deviation (SD) of that population. High scores mean more of the concept being measured. The domain-specific approach is based on the idea that health attributes, such as pain and

physical function are not unique to a specific disease. The PROMIS contains a bank of questions from which relevant items can be extracted and used to create a custom form. The PROMIS Pain Interference, Physical Function Mobility, and Fatigue domain scores will be administered to subjects ≥ 5 years of age at the Screening Visit. To assess these health domains, items from the Pediatric Pain Interference, Physical Function Mobility, and Fatigue item banks (Version 2.0) were extracted to develop a self-report form that will be completed by children 8 years of age and older at the Screening Visit. For children ages 5 to < 8 years at the Screening Visit, the same items were extracted from the Parent Proxy item banks (Version 2.0) that will be completed by the parent or legal guardian. The Parent/Legal Guardian form will be used for the duration of the study for subjects < 8 years of age at the Screening Visit, even when a subject turns 8 during the study. The answers collected from PROMIS questionnaire will be uploaded to the PROMIS online scoring system <http://www.healthmeasures.net/explore-measurement-systems/promis> to obtain the final scores for Pain Interference, Physical Function Mobility, and Fatigue domain.

5.11 Faces Pain Scale – Revised (FPS-R)

Pain intensity will be self-reported by subjects using the Faces Pain Scale – Revised (FPS-R) for subjects ≥ 5 years of age at the Screening Visit. The FPS-R is a self-reported measure of pain intensity developed for children (Hicks et al. 2001). It was adapted from the Faces Pain Scale (Bieri et al. 1990) to make it possible to score the sensation of pain on the widely accepted 0-to-10 metric. The FPS-R has been validated for use in children 5 to 16 years of age. The FPS-R graphically depicts pain intensity using faces with scores chosen from 0, 2, 4, 6, 8, and 10 (0=no hurt; 10=hurts worst).

5.12 Blood Pressure and Blood Pressure Percentile

BP will only be collected for subjects who are ≥ 3 years old. At Screening and Baseline the blood pressure will be measured three time at both pre and post study visit assessment. After Baseline the blood pressures will be measured three times at pre-assessment only. At each visit, the average blood pressure will be calculated and used for analysis.

The blood pressure percentile will be derived based on the forth report on the diagnosis, evaluation and treatment of high blood pressure in children and adolescents (NHLBI 2005). See Appendix 7 for details in deriving blood pressure percentile adjusting for age, gender and height.

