14. Vital sign measurements consist of seated systolic/diastolic blood pressure (BP) measured in millimeters of mercury (mm Hg), heart rate (beats per minute), respiration rate (breaths per minute), and temperature in degrees Celsius (°C). Vital signs will be obtained at the beginning of each visit before any additional assessments are completed and after the subject has rested for 5 minutes. BP measurements will only be obtained at clinic visits and only for subjects ≥ 3 years of age. At the Screening Visit and at Baseline, 2 sets of 3 BP measurements will be obtained – the first set will be done at the beginning of the visit and the second set at end of the visit after all site procedures are completed. BP measurements should be obtained by auscultation (ie, manually and without using an automated device) after the subject has rested for 5 minutes and a second and third BP measurement should be obtained, each performed 30 seconds apart.
15. The subject's weight collected at in-clinic visits will be the basis of the KRN23 dose calculation until the next in-clinic weight collection.
16. Adverse events and concomitant medications information will be collected at HH visits for subjects in the KRN23 arm during the Treatment Period and for all subjects during the Treatment Extension Period (HH visits are not applicable to subjects in Japan or Korea). For subjects in the active control arm during the Treatment Period, adverse events and concomitant medications information will be collected by telephone call.
17. Serum chemistry panels may include PD parameters (ie, serum phosphorus and ALP), and safety parameters of interest (ie, calcium) to avoid duplication of testing.
18. Both 2-hr and 24-hr urine will be used for measurements of urinary phosphorus, creatinine, and calcium; 2-hr urine will be used for the derivation of TmP/GFR and TRP. For subjects < 5 years of age, spot urine may be collected in place of the 2-hr urine samples for measurements of urinary calcium, phosphorus, and creatinine.
19. Separate dental assessments are not required and will be captured under AEs as dental issues arise. At each clinic visit, an oral examination will be conducted and subjects will be proactively asked if they had any dental events such as dental caries, tooth extraction, root canal, dental abscesses, and gingivitis.
20. Pregnancy testing will be performed on any female subject of childbearing potential who has experienced menarche.

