7.5.3.2 Vital Signs Including Standardized Blood Pressure Measurement Procedure

Vital signs will include seated systolic blood pressure and diastolic blood pressure measured in millimeters of mercury (mm Hg), heart rate in beats per minute, respiration rate in breaths per minute, and temperature in degrees Celsius (°C). Blood pressure (BP) measurements will only be obtained at clinic visits and only in children ≥ 3 years of age at the Screening Visit. Children who turn 3 years of age during the study will start BP assessments at the next scheduled clinic visit and continue with subsequent scheduled BP assessments for the duration of the study. The guidance provided by The Fourth Report on the Diagnosis, Evaluation, and Treatment of High Blood Pressure in Children and Adolescents (NIH 2005) will be used as a reference.

Vital signs measurements will be obtained at each indicated visit (Table 2.1, Table 2.2, and Table 2.3). On the Screening and Baseline Visit, 2 sets of 3 BP measurements will be obtained - the first set will be done at the beginning of the visit and the second set at end of the visit after all site procedures are completed. BP measurements should be done after the

subject has rested for 5 minutes and a second and third BP measurement should be obtained, each performed 30 seconds apart. Thus there will be a total of 6 BP measurements on these 2 visits. As part of the site initiation visit, standardized BP measurement training will be provided to all study personnel responsible for BP measurement and appropriate documentation in monitoring report. In addition, evidence of annual calibration of BP measurement device will be documented.

Participants are instructed to refrain from exercise at least 30 minutes before and until completion of BP measurement. They are also instructed to refrain from playing video games, or other activities that may affect BP until all measurements are obtained. Clinic BP measurements are obtained in the right arm of the study participant. At each study visit, before BP determination, arm circumference is measured (in centimeters) with a plastic measuring tape at the midpoint of the upper arm between the acromium (tip of shoulder) and olecranon (tip of elbow) and a cuff is then selected so that the length of the cuff bladder is equal to 80% to 100% of the arm circumference. Effort should be made to use the same BP measuring device for BP measurements during subsequent visits.

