After 5 minutes of rest, pulse and BP measurements begin. The cuff is inflated approximately 30 mm Hg above the pressure when the radial pulse is no longer felt. The BP measurements are obtained by auscultation (ie, manually and without using an automated device) of the brachial artery using the first Korotkoff sound for systolic BP (SBP) and the fifth Korotkoff sound for diastolic BP (DBP). Three BP measurements are obtained at a sitting and recorded in the participant's BP records for the study visit. For the subsequent site visits post-baseline, 3 BP measurements is recorded during the site visit.

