5 DEFINITIONS

5.1 Baseline

Baseline is defined as the last assessments prior to or on the date of initiation of the first dose of investigational product.

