8.8.3 Vital Signs

Descriptive statistics for vital signs (systolic and diastolic blood pressures, systolic and diastolic blood pressure percentiles, pulse rate, and weight) and changes from baseline values at each visit and at the end of study will be presented by treatment group.

The blood pressure will be summarized by study visit in mmHg and percentile to assess the blood pressure change over time.

Heart rate and heart rate percentile category will be tabulated over time by treatment group.

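### Baseline blood pressure pools start-of-visit and end-of-visit readings while later visits use start-of-visit readings only, so change from baseline is not like for like (minor).

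*SAP*

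**What the plan says.** SAP 5.12 sets the measurement plan. For the first two visits: "At Screening and Baseline the blood pressure will be measured three time at both pre and post study visit assessment". For later visits: "After Baseline the blood pressures will be measured three times at pre-assessment only". It then gives the rule for analysis: "At each visit, the average blood pressure will be calculated and used for analysis". It does not say that the Baseline average is restricted to one of the two sets.

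The protocol agrees on the counts. Section 7.5.3.2 says of Screening and Baseline: "Thus there will be a total of 6 BP measurements on these 2 visits". For later visits it says: "For the subsequent site visits post-baseline, 3 BP measurements is recorded during the site visit". Footnote 14 to the protocol's Schedule of Events places "the second set at end of the visit after all site procedures are completed", and footnote 13 to the SAP's copy of the schedule places it at the same point.

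SAP 5.1 gives the general definition: "Baseline is defined as the last assessments prior to or on the date of initiation of the first dose of investigational product". SAP 8.8.3 covers systolic and diastolic pressure and their percentiles: "changes from baseline values at each visit and at the end of study will be presented by treatment group". SAP 4.3 lists change from baseline in vital signs as a safety endpoint.

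**The concern.** A change from baseline is interpretable when both values are measured under the same conditions. Here half of the Baseline average comes from the end of a long visit and none of any follow-up average does. The protocol itself treats conditions around the reading as important: section 7.5.3.2 asks children to avoid exercise and other activities that could affect blood pressure until measurement is finished. The Week 0 column of the schedule nevertheless includes blood sampling, an ECG and, from age 5, a six-minute walk test.

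Any systematic difference between the start and end of the visit would enter every follow-up change with the same sign. It would look like a sustained change during treatment, and a larger sample would not remove it.

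**Working it through.** **Counts.** Screening and Baseline: 2 sets x 3 readings = 6 per visit, which matches protocol 7.5.3.2. Each later visit: 1 set x 3 readings = 3.

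**Artefact within an arm.** Let A be the expected start-of-visit pressure and A + d the expected end-of-visit pressure at Baseline.

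- Baseline mean of six: [3A + 3(A + d)]/6 = A + d/2.
- Follow-up mean of three with no true change: A.
- Change from baseline: A - (A + d/2) = -d/2.

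**Size.** d is not in the documents. As an assumption I take -6 to +6 mmHg, symmetric because the direction is also unknown.

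| d (mmHg) | Artefact in change from baseline (mmHg) |
|---|---|
| -6 | +3 |
| -2 | +1 |
| 0 | 0 |
| +2 | -1 |
| +6 | -3 |

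SAP Appendix 7 gives a systolic SD of 10.7128 mmHg for boys and 10.4855 for girls. At the ends of the range, 3/10.7128 = 0.28 SD and 3/10.4855 = 0.29 SD. For a child at the median, Phi(0.28) - 0.5 = 0.11, or about 11 percentile points. The shift in percentile is smaller further from the median.

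**Do other SAP rules remove the mismatch?**

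- SAP 5.1 sets baseline by date, with no clock-time cut-off. The end-of-visit set falls on the qualifying date and is not excluded.
- SAP 7.2.3 says that, when several values fall on one day, the latest is used in descriptive tables. Applied here it would leave only end-of-visit data, and the artefact would double to -d. I take the specific averaging rule in 5.12 to govern, but the two rules give different baselines.

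**Between arms.** With d_K in the KRN23 arm and d_C in the control arm, the difference between arms in change from baseline shifts by -(d_K - d_C)/2. This is zero in expectation if the second set is taken under the same conditions in both arms.

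**Order of dosing and the second set.** Two statements in the same schedule point in different directions:

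- Footnote 14 puts the second set after every site procedure, and the schedule marks KRN23 administration at Week 0. Together these suggest a post-dose set in the KRN23 arm.
- Footnote 1 requires all Screening and Baseline assessments to be satisfied before randomization and dosing. The second blood pressure set is a Baseline assessment, so this suggests a pre-dose set.

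No passage states the order outright.

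**After the fix.** With the three start-of-visit readings as baseline, the expected change is A - A = 0 for any d, and both sides of the subtraction average three readings.

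**The case against.** A reader might infer that the second Baseline set follows the first KRN23 injection, and that the comparison between arms is therefore biased. The documents do not support that as a finding. It rests on the Week 0 dosing mark read together with footnote 14, and footnote 1 points the other way. The injection is the only arm-specific mechanism on offer. If the set is pre-dose, both arms follow the same procedure and the artefact should largely cancel in the comparison with control. If it is post-dose, it may not cancel, but the documents give no figure for the difference between d_K and d_C.

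Three further points count against a strong concern, and all stand:

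- The size is wholly assumed. The protocol's five-minute rest, its ban on exercise from 30 minutes before until measurement is complete, and its standardised technique should all reduce d. The 3 mmHg is the edge of an assumed range, not an expected effect.
- The output is descriptive. SAP 8.8 and 8.8.3 plan no hypothesis test or decision threshold for blood pressure, and it is not among the events to monitor in SAP 5.15.
- Observed pressures and percentiles are also tabulated by visit and arm. Those follow-up values come from start-of-visit readings in both arms and do not use the Baseline average.

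It can also be said that 5.12 never states in words that all six readings are averaged. That is true, but it is the plain reading, and the same-day rule in 7.2.3 would not give a matched baseline either. The mismatch survives the objections; the claim of bias between arms does not.

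**Conclusion.** The point holds as a minor one, with moderate confidence. Under the SAP's own averaging rule, Baseline blood pressure and follow-up blood pressure are measured at different points in the visit, and no other rule corrects this. Each within-arm change from baseline carries -d/2: at most 3 mmHg, about 0.28 systolic SD, if d lies between -6 and +6 mmHg.

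This rests on two assumptions: that 5.12 averages all six Baseline readings, and the stated range for d. Neither a post-dose second set nor a bias between arms is established.

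The effect is confined to descriptive summaries of blood pressure and its percentiles in children aged 3 years or older with a Baseline reading. Children who start blood pressure assessment on turning 3 during the study have no Baseline reading and contribute no change. The primary endpoint, sample size and alpha are untouched.

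**What to change.** In SAP 5.12, define Baseline blood pressure as the mean of the three start-of-visit readings at the Baseline visit, and state that this takes precedence over the same-day rule in 7.2.3. Summarise or list the end-of-visit set separately; its difference from the start-of-visit set also gives a direct estimate of d. Footnotes 1 and 14 of the schedule should be reconciled on when the second set falls relative to dosing, so that the separate summary can be labelled correctly.

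No new data are needed. The cost is that the Baseline mean uses three readings instead of six, so it is slightly noisier, though it then averages the same number of readings as each follow-up mean.
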